### 3.2 Key Definitions

- **Baseline:** The baseline value is defined as the last available valid (quantifiable continuous or categorical value), non-missing observation for each participant prior to first study drug administration. Repeat and unscheduled assessments will be included in the derivation of the baseline values.
- **Change from Baseline:** The change from baseline value is defined as the difference between the result collected/derived at a post-baseline visit/time point and the baseline value.

The change from baseline value at each post-baseline visit/time point will be calculated for all continuous parameters using the following formula:

$$\text{Change from Baseline Value} = \text{Result at Visit/Time Point} - \text{Baseline Value}$$

The change from baseline value will only be calculated if the specific post-baseline visit/time point result and the baseline value for the parameter are both available and will be treated as missing otherwise.

- **Percent Change from Baseline**

Percent Change from Baseline at each post-baseline visit/time point will be calculated for all continuous parameters using following formula

$$\% \text{ Change from Baseline} = 100 \times \frac{(\text{Post-Dose Visit Value} - \text{Baseline})}{\text{Baseline}}$$

- **Study day:** The study day of an event is defined as the relative day of the event starting with the date of the first study drug administration (reference date) as Day 1 (there will be no Day 0).

Relative days for an event or measurement occurring before the date of first dose will be calculated as follows:

$$\text{Relative Day} = \text{Event Date} - \text{Date of First Dose}$$

The relative day for an event or measurement occurring on or after the reference date to the date of the last dose will be calculated as follows:

$$\text{Relative Day} = \text{Event Date} - \text{Date of First Dose} + 1$$

There is no relative Day 0. Relative day will not be calculated for partial dates in cases where relative day is shown in a data listing.

### 3.3 Hypothesis Testing

No inferential analysis will be included.

### **3.4 Multiple Comparisons and Multiplicity Adjustments.**

Not applicable.

### **3.5 Handling of Dropouts or Missing Data**

Missing, unused, or spurious data will be handling in the following manner:

- There will be no imputations or substitution made for missing safety data points.
- For the PK analyses, imputations will be made for missing data points as noted in section 9.

For TEAEs and concomitant medications determination, the following rules will be followed:

- a. If the date/time is present, the full date/time will be compared to the date/time of first study drug administration.
- b. If time is missing (start and/or end time), the event/medication dates will be used for TEAE/concomitant medication determination. I.e. if the event/medication have the same start/stop date as the Adverse Event (AE)/medications, the event/medication will automatically be classified as a TEAE/concomitant medication (unless a partial time confirms the event/medication to have started/been given pre or post treatment).
- c. If dates are completely missing (start and end dates), the event/medication will automatically be classified as a TEAE/concomitant medication.
- d. For TEAEs, if the event end date (time) is prior to first study drug administration, the event will not be classified as a TEAE. For concomitant medications, if the medication start date (time) is post the first study drug administration, the medication given will be classified as a Concomitant medication.
- e. If only the AE start year/concomitant medication end year is present and is the same or is after the first study drug administration year unit, the event/medication will be classified as a TEAE/Concomitant medication.
- f. If the TEAE start month and year/concomitant medication end month and year are present and are the same or after the first study drug administration month and year combination, the event/medication will be classified as a TEAE/Concomitant medication.

#### Conversion of categorical values

In some instances, continuous variables are expressed as a range (i.e. < 10). In such cases these values may be converted to a continuous value. The rule for expression such values are as follows:

- Value = the categorical boundary
- As an example, a value of <10 may be converted to 10
- Such substitutions will be clearly documented in the footnotes of relevant outputs.

All other data will be analysed as collected and missing values will not be imputed nor replaced.

#### End of Study (EOS) vs. Early Termination (ET)

For any analyses based on safety data, data for participants that terminates the study early (ET assessments) will be summarised with the EOS assessments of participants that complete the study as planned.

### **3.6 Coding of Events and Medications**

Adverse event verbatim terms will be coded using the Medical Dictionary for Regulatory Activities (MedDRA) Version 23.0 or the latest version in use. Terms will be coded to the full MedDRA hierarchy, but the System Organ Class (SOC) and Preferred Terms (PT) will be of primary interest for the analysis.

Prior and concomitant medications will be coded using the World Health Organization Drug Dictionary (WHO-DD, Sep-2019) or the latest version in use. Medications will be mapped to the full WHO-DD Anatomical Therapeutic Chemical (ATC) class hierarchy, but PTs will be of primary interest in this analysis.

### **3.7 Treatment assignment and treatment groups**

TFLs will be presented by treatment groups, and for all study participants in the given analysis set, where applicable.

The following order will be used in the TFLs (with the treatment arm displayed, as applicable to the output):

- Part A: 3000 mg LMN-101
- Part B: 300 mg LMN-101 PO TID
- Part B: 1000 mg LMN-101 PO TID
- Part B: 3000 mg LMN-101 PO TID
- Part B: LMN-101 Overall
- Part B: Placebo
- Overall

## **4. ANALYSIS SETS**

In this study, two analysis sets are defined: The Safety and PK Analysis Sets.

Any additional exploratory analysis not specified in the SAP will be identified in the final CSR as exploratory post hoc analyses. This may include the addition of additional study populations or subgroups of interest.

The number and percentage of participants in each analysis set will be summarized.

### **4.1 Analysis Sets Descriptions**

#### **4.1.1 Safety Analysis Set**

The safety analysis set will be defined as a modified Intention-to-treat (mITT) analysis set which will include all randomized participants meeting inclusion criteria who receive at least one dose of study drug. The safety analysis set will be based on actual treatment received if different from randomized treatment.

#### **4.1.2 Pharmacokinetic (PK) Analysis Set**

The PK analysis set will be defined as a per Protocol population which consists of all randomized subjects who complete the full course of study drug and who have an adequate quantifiable and interpretable serum concentrations of VHH. Subjects with protocol violations to be assessed on a subject-by-subject basis for inclusion in the PK Population. The sponsor will confirm the eligibility of subjects after a review of the serum concentrations data of VHH. Patients who receive only placebo will be excluded from the PK set. PK parameters will be excluded from the analysis and summary statistics where there are inadequate serum concentrations of VHH. PK analysis of serum VHH will be conducted using the Pharmacokinetic analysis set.

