7 STUDY PROCEDURES

7.1 Duration of Study Drug Treatment

The duration of study drug treatment will be for one dose for Part A and for 4 weeks for Part B. All subjects in Part B will receive a total of 84 doses.

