## **6. PROTOCOL DEVIATIONS**

Protocol deviations will be presented for each participant in the by-participant data listings for the enrolled set. All data will be listed (by-participant listings) by treatment group.

Prior to database lock, all protocol deviations will be reviewed by medical monitors and assigned a status of important protocol deviation/or not.

Protocol deviations may include, but are not limited to the following:

- Violation of inclusion/exclusion criteria
- Missed or out of window assessments
- Non-compliance to study treatment
- Use of prohibited concomitant medications, treatments or procedures
- Deviation from study specific instructions.

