**Programming Note:**

- Include all treatment groups: Part B: LMN-101 300 mg, Part B: LMN-101 1000 mg, Part B: LMN-101 3000 mg, Placebo.

Sponsor: Lumen Bioscience, Inc.  
Protocol: CAM01

Database Lock: yyyy-mm-dd

Table 14.2.1.1 Summary of Serum Concentrations of VHH by Timepoint (PK Analysis Set)

Treatment Group Timepoint	Actual Value (unit)							
	n	n BLQ	Mean	SD	Median	Minimum	Maximum	CV%
Part A: LMN-101 3000 mg (N=xx)								
Day 1 Pre-dose 	xx	xx	xx.xx	xx.xx	xx.xx	xx.x	xx.x	xx.xx
Day 1 2h Post-dose	xx	xx	xx.xx	xx.xx	xx.xx	xx.x	xx.x	xx.xx
Day 2	xx	xx	xx.xx	xx.xx	xx.xx	xx.x	xx.x	xx.xx
Part B: LMN-101 300 mg (N=xx)								
Day 1 Pre-dose 	xx	xx	xx.xx	xx.xx	xx.xx	xx.x	xx.x	xx.xx
Day 1 2h Post-dose	xx	xx	xx.xx	xx.xx	xx.xx	xx.x	xx.x	xx.xx
Day 2	xx	xx	xx.xx	xx.xx	xx.xx	xx.x	xx.x	xx.xx
Day 8	xx	xx	xx.xx	xx.xx	xx.xx	xx.x	xx.x	xx.xx
Day 28	xx	xx	xx.xx	xx.xx	xx.xx	xx.x	xx.x	xx.xx
Day 29	xx	xx	xx.xx	xx.xx	xx.xx	xx.x	xx.x	xx.xx
Part B: LMN-101 1000 mg (N=xx)								
Day 1 Pre-dose 	xx	xx	xx.xx	xx.xx	xx.xx	xx.x	xx.x	xx.xx
Day 1 2h Post-dose	xx	xx	xx.xx	xx.xx	xx.xx	xx.x	xx.x	xx.xx
Day 2	xx	xx	xx.xx	xx.xx	xx.xx	xx.x	xx.x	xx.xx
Day 8	xx	xx	xx.xx	xx.xx	xx.xx	xx.x	xx.x	xx.xx
Day 28	xx	xx	xx.xx	xx.xx	xx.xx	xx.x	xx.x	xx.xx
Day 29	xx	xx	xx.xx	xx.xx	xx.xx	xx.x	xx.x	xx.xx

etc.

SD: Standard Deviation; CV: Coefficient of Variation

Baseline is defined as the last valid, non-missing assessment prior to study drug administration on Day 1.

nBLQ: number of datapoints below the quantifiable limit

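### The PK analysis set is selected on quantifiable VHH, so with partial absorption the concentration table, listing and figures omit dosed participants who have only BLQ values; SAP 13 also puts antibodies on this set, against the SAP's own output labels

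*SAP*

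**What the plan says.** SAP 4.1.2 defines the PK set as "all randomized subjects who complete the full course of study drug and who have an adequate quantifiable and interpretable serum concentrations of VHH". It leaves out participants who received only placebo. On the remaining decisions it says:

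- For violations of the protocol, each case is judged on its own, with no stated criterion.
- For confirmation of membership: "The sponsor will confirm the eligibility of subjects after a review of the serum concentrations data of VHH"
- For inadequate data: "PK parameters will be excluded from the analysis and summary statistics where there are inadequate serum concentrations of VHH"

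The last rule works at the level of the PK parameter and is separate from set membership.

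SAP 9 runs the PK analysis on this set if absorption is indicated. SAP 17 to 19 and the shells label Table 14.2.1.1, Listings 16.2.6.1 and 16.2.6.2 and all eight VHH figures with it. For concentration summaries SAP 9 sets BLQ to zero and adds a BLQ count, which the shell of Table 14.2.1.1 explains as "nBLQ: number of datapoints below the quantifiable limit". For plots and PK parameters it uses another rule: BLQ is zero before the first quantifiable value and missing after it. SAP 9 and 9.1 also say that all PK data, and VHH levels at every collected time point, will be listed.

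SAP 13 places immunogenicity on the PK set. SAP 17, SAP 18 and the shells label the antibody tables and listings Safety, and the programming note to Table 14.4.1 includes placebo. SAP 9.1 asks for placebo in the VHH figures; the figure shells leave it out.

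**The concern.** Protocol 3.4 says that serum levels are measured to find out whether this oral protein is absorbed at all. Absorption is not expected, so a mixture of BLQ-only and quantifiable participants is a realistic way for the PK analysis to be triggered. In that case the BLQ-only participants are part of the answer, yet membership of the set depends on the very value being summarised. The reported mean then describes people selected for having measurable VHH. The zero rule and the BLQ count cannot reach anyone outside the set, and Listing 16.2.6.2 as labelled would not carry data that SAP 9 and 9.1 promise to list.

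The completion condition may also remove valid first-dose samples from people who stop early, although peak and AUC after the initial dose are secondary endpoints. For antibodies, two populations are specified, and only one has a placebo comparison.

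**Working it through.** **Inputs.** Planned enrolment (SAP 2.1) is 2 in Part A plus three cohorts of 4 active and 2 placebo: 2 + 3 × (4 + 2) = 20, of whom 2 + 12 = 14 receive LMN-101 and 6 placebo. This agrees with the stated total. The documents give no figure for q, the fraction of a dosed group with any quantifiable VHH, so q is varied. Part A is counted as eligible because the PK shells show it.

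**Table mean.** Assume all complete and are sampled. BLQ-only participants contribute 0 at every time point, so

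mean(all dosed) = q × mean(PK set), and mean(PK set) / mean(all dosed) = 1/q.

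With an illustrative 10 units for each quantifiable participant:

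| Values | PK-set mean | All-dosed mean | Ratio |
|---|---|---|---|
| 10, 0, 0, 0 | 10 | 2.5 | 4.0 |
| 10, 10, 0, 0 | 10 | 5 | 2.0 |
| 10, 10, 10, 0 | 10 | 7.5 | 1.33 |
| 10, 10, 10, 10 | 10 | 10 | 1.0 |
| 10, 0 (Part A) | 10 | 5 | 2.0 |

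In the first row the median moves from 0 to 10, and with one member left no SE can be computed for the figures. If nobody in a cohort is quantifiable, the cohort disappears from the table.

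**BLQ count.** If every PK-set member is quantifiable at 2 h, the first three rows print n = 1, 2 or 3 with a BLQ count of 0, in place of n = 4 with 3, 2 or 1. A member who is quantifiable only on a later day is BLQ at 2 h and is counted, so the count is not always zero.

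**Figures.** Take one member at 10, one member now BLQ after an earlier quantifiable value, and two BLQ-only participants (q = 2/4).

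- Table rule: (10 + 0)/2 = 5 against 10/4 = 2.5, ratio 2 = 1/q.
- Plot rule: the second member is missing, so 10 against (10 + 0 + 0)/3 = 3.33, ratio 3.

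The factor 1/q therefore need not apply to the figures.

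**Non-completers.** Take 2 h values of 30, 10, 10 and 0, where the 30 belongs to a non-completer and the 0 to a BLQ-only participant. The PK-set mean is (10 + 10)/2 = 10 and the all-dosed mean is 50/4 = 12.5, a ratio of 0.8, whereas 1/q would give 4/3 = 1.33. The direction can reverse. A Part B participant who stops after the Day 8 visit has already had 4 of the 6 scheduled PK samples (pre-dose, 2 h, 24 h, Day 8).

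**How readily this occurs.** If each participant independently has probability p of any quantifiable value, the chance that a cohort of 4 loses at least one is 1 − p⁴: 0.996, 0.938, 0.684 and 0.344 for p = 0.25, 0.50, 0.75 and 0.90. These values of p are assumptions.

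**Antibodies.** The Safety set allows up to 20 participants including 6 on placebo. The PK set allows at most 14 and no placebo, less any BLQ-only participants and non-completers.

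**The case against.** The best defence is that the exclusion can be seen. SAP 4, SAP 5.1.1 and the shell of Table 14.1.1 give the number and percentage in each analysis set by treatment group, and Table 14.2.1.1 prints N. That stands: a reader could see that 1 of 4 is in the PK set. But the shell does not separate BLQ-only exclusion from non-completion or protocol violations, and Listing 16.2.1.1 shows membership without concentrations, so the mean cannot be corrected from it.

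It is also fair that SAP 9 already requires all PK data to be listed, that every antibody output is labelled Safety, and that SAP 13 itself mentions only listings. The antibody point is therefore a conflict of wording to be settled, not evidence that placebo would in fact be dropped.

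Some stronger readings are tempting but not supported:

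- That a single missed dose removes a participant. SAP 4.1.2 provides case-by-case assessment of violations, SAP 6 lists "Non-compliance to study treatment" among deviations reviewed before database lock, and Protocol 7.14 gives four or more missed doses as its example of non-compliance.
- That SAP 14 conceals a departure from the protocol. The per-protocol population in Protocol 7.15 is tied to the primary endpoint, the protocol defines no PK set, and Protocol 7.18 already makes PK summaries depend on detection. The clarification letter cited in SAP 20 is not among the documents.
- That the sponsor selects members with treatment codes open. SAP 15.2 names approval of the analysis sets ahead of unblinding in its conditions for the final analysis. What remains is that the concentrations themselves are seen first, with no definition of adequate.
- That early stoppers simply shrink the cohort. Those with less than three weeks of drug are replaced, except in Cohort 3 (SAP 2.4). Replacement does not, however, return the first participant's samples to the summary.

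**Conclusion.** The point holds. As written, the set selects on the quantity being summarised, and this defeats the SAP's own BLQ and listing rules. The parameter-level exclusion in SAP 4.1.2 already protects the parameter estimates, so the set-level condition is not needed for that.

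The overstatement of 1/q, between 1.33 and 4.0-fold for 3 down to 1 of 4 quantifiable, applies to the arithmetic mean at a table time point and assumes that all participants complete and are sampled. It is 1.0 if all absorb, and the question does not arise if none do. It should not be carried over to the figures, and loss of a quantifiable non-completer can turn it the other way.

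A reader might infer that the safety conclusions or the decision whether to run PK and antibody work are compromised. They are not: safety uses the Safety set, and the SAP 15.1 decision rests on the interim concentration dataset, for which the PK set is not named. The affected outputs are conditional, descriptive and secondary. They should be corrected because the error is in a stated rule and costs little to remove.

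**What to change.** 1. Define a PK concentration set: all LMN-101-dosed participants in Parts A and B with at least one post-dose serum result, BLQ retained. Use it for Table 14.2.1.1, Listings 16.2.6.1 and 16.2.6.2 and the VHH figures. Update SAP 4 (which names two sets), Table 14.1.1 and Listing 16.2.1.1 to match. In the log10 figures, give by footnote the number of participants with only BLQ values, since zeros cannot be drawn.
2. Apply quantifiability and completion only to PK parameters, by rules fixed before the concentrations are reviewed. Day 1 parameters should not require completion of the course. Report the number without a quantifiable value beside each summary.
3. Change SAP 13 to the Safety set including placebo, in line with SAP 17, SAP 18 and the shells.
4. Reconcile the request for placebo in the VHH figures (SAP 9.1) with the figure shells, which omit it.

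The cost is SAP wording, one added analysis set and a few relabelled outputs, with no new samples. The concentration summaries will contain more zeros.

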## **5. PARTICIPANT DISPOSITION AND ANALYSIS POPULATIONS**

Outcomes will be summarized as noted in section 3.1 by treatment group and will be based on the safety analysis set. All data will be listed by treatment group.

### ***5.1.1 Participant Disposition***

A detailed description of participant accountability will be generated by treatment group including count of:

- Number of participants screened.
- Number of participants randomized.
- Number (%) of participants who terminated the study early and the primary reason for early termination.
- Number (%) of participants included in each analysis set.

A listing of participant disposition with study discontinuation will be presented. Reason for consent withdrawal, date of death, primary reason for death and whether an autopsy was performed will also be listed.

Screening failures and reason for screening failure, will be noted in the listing of eligibility criteria. All withdrawals from the study, taking place on or after study drug administration, will be fully documented in the body of the clinical study report (CSR).

## **6. PROTOCOL DEVIATIONS**

Protocol deviations will be presented for each participant in the by-participant data listings for the enrolled set. All data will be listed (by-participant listings) by treatment group.

Prior to database lock, all protocol deviations will be reviewed by medical monitors and assigned a status of important protocol deviation/or not.

Protocol deviations may include, but are not limited to the following:

- Violation of inclusion/exclusion criteria
- Missed or out of window assessments
- Non-compliance to study treatment
- Use of prohibited concomitant medications, treatments or procedures
- Deviation from study specific instructions.

## **7. DEMOGRAPHIC AND BASELINE INFORMATION**

Demographic and baseline information will be summarized as noted in section 3.1 by treatment group and will be based on the safety analysis set.

### **7.1 Demographics**

#### **7.1.1 Endpoints**

- Age (years)
- Sex
- Race
- Ethnicity
- Childbearing Potential (as a % of all female participants)
- Height (cm)
- Weight (kg)
- BMI (kg/m^2)

### **7.2 Medical history**

Medical history will be coded using medical dictionary for regulatory activities (MedDRA®) and will be listed.

### **7.3 Serology (HIV/HBsAg/HCV Ab)**

The following viral detection results (serologies) at Screening, will be listed for each participant: HIV 1 Antibody/ HIV 2 Antibody, HBsAg and HCV Antibody.

### **7.4 Urine Drug Test**

Urine drug test screen/results at Screening will be listed for each participant.

### **7.5 Informed Consent and Eligibility**

Informed consent date and inclusion/exclusion eligibility criteria information, including any criteria not met, will be listed for each participant.

## 8. STUDY DRUG ADMINISTRATION

Study drug administration results and drug accountability will be presented based on the safety analysis set.

Two by-participant data listings will be generated for study drug administration. The first listing will include date and time of administration, participant fasting status 1 hour before and after dosing, dose per administration and whether the dose was given per protocol for Day for Parts A and B.

Drug accountability over the complete course will be listed for Part B and will include date dispensed/returned, missed doses, date of missed dose, dose size missed, reason for missed dose, type of tablet dispensed, and number of tablets dispensed. Study drug compliance will be calculated by participant as follows:

$$\text{Study Drug Compliance}(\%) = \left(1 - \frac{\# \text{ Tablets returned}}{\# \text{ Tablets dispensed}}\right) * 100$$

## 9. PHARMACOKINETICS (PK)

Pharmacokinetics will be analyzed using the PK analysis set. If VHH concentration determination of serum samples indicates systemic absorption, then PK analysis will be performed on serum VHH concentration data.

The serum levels of VHH will be determined for both Part A (a single dose treatment) and Part B (MAD, thrice daily treatment) groups before the first dose (pre-dose) and at 2 hours (Day 1), and 24 hours (Day 2) after the first post-dose. If serum levels of VHH are quantified, serum pharmacokinetics of VHH will be determined and summarized.

The serum levels of VHH will be determined for Part B (MAD, thrice daily treatment) groups on Day 8, day 28 and day 29. If serum levels of VHH are quantified and systemic absorption is observed serum pharmacokinetics of VHH will be determined and reported.

All PK data collected at scheduled and unscheduled visits will be included in the listings, but only results collected as scheduled visits will be included in the summary tables.

Stool samples will be collected, and supernatant stored for potential future analysis if required. Fecal concentrations of VHH will be considered and analyzed (based on new SAP) if requested or recommended by the Regulatory Authority.

